## 1. Purpose of the Study / Objectives

The purpose of this study is to determine if IO morphine decreases pain, inflammatory markers, and post-operative opioid use in total knee arthroplasty (TKA) patients.

- Aim 1: IO morphine will significantly reduce patient pain in the post-operative period after primary TKA.
  - Sub aim: IO morphine will cause significantly higher levels of morphine within the joint compared to current standard of care.
- Aim 2: IO morphine will decrease systemic inflammatory markers in the post-operative period after primary TKA.
- Aim 3: IO morphine will result in significantly less post-operative oral opioid use, and achieve superior outcomes such as increased range of motion (ROM).

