### **Exclusion criteria**

- Patient lacks the capacity to consent to the research project (study will not utilize LAR signatures during the informed consent process)
- Weigh < 100 pounds
- BMI > 38
- Pregnancy or suspected pregnancy
- Past medical history of opioid addiction.
- Established hypersensitivity (ie allergy) to morphine.
- Acute or chronic liver disease for example cirrhosis.
- Use of any narcotics 5 days before surgery (opioids, hydrocodone, morphine, hydromorphone, fentanyl, etc).
- Undergoing bilateral total knee replacement, revision total knee arthroplasty, or any additional procedure outside of a primary total knee arthroplasty.
- Unable to get general and spinal anesthesia.
- Same-day discharge on day of surgery.

We will access the following data from medical records (Epic) including PHI:

- MRN, date of surgery, age, gender, past medical history, height, weight, BMI, laterality, pre-operative ROM, pre-operative pain VAS, intra-operative tourniquet pressure, procedure duration, and medications received during hospital stay.

Post-operatively we will ask study patients in both groups to complete a post-op symptom journal that will collect the following information in the interim before the patient's standard 2 week post op appointment with [name], [name], or [name]:

- Record daily pain levels using a validated pain scale for 14 days post op.
- Record daily pain medication use for days 14 post-op.
- Record daily nausea levels using a validated scale as well as recording bowel movements and any instances of emesis for 7 days post op.

Additionally, the tourniquet pressure intra-op will be standardized to 275 mmHg across all 3 providers on the research team (Drs. [name], [name], and [name]). This falls within the normal standard of care for all 3 providers for their total knee arthroplasty patients. However, it has been shown in the literature that tourniquet pressure can influence acute post-operative muscle quality including increased pro-inflammatory cytokines. Therefore, to limit outside factors on post-operative inflammatory marker levels as well as post-operative rehabilitative outcomes the research team will use the same tourniquet pressure for all study patients. This does not reflect an elevation in risk for study patients since 275 mmHg falls within range of standard of care for total knee arthroplasty patients for all 3 providers.

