### **Baseline and Post-op Blood Samples:**

Systemic sample – Blood draws will only be done with [name] patients that decide to participate in the study if they are the first or second case of the day. Three blood draws will be taken in these patients including just after induction of anesthesia, 15 minutes after the tourniquet is released, and 10 hours post op. The 10hr post-op blood draw timing will be based on the timing of the intraosseous injection. Serum samples will be used to measure inflammatory cytokines IL-6 and IL-8, and expression of CD11a, CD11b, CD11c, and CD18 as well as the systemic level of morphine present in the blood. Only these specific study patients will be having blood draws done due to the 10 hr post-op draw needing to be processed within 30 minutes of the draw. Blood samples will be collected in EDTA glass tubes by Houston Methodist nursing staff or a qualified member of the research team (eg. physician, fellow, or resident). Up to 10 ml of blood will be collected per time point.

For our primary outcome variable of VAS recorded pain, power analysis was performed using JMP statistics software utilizing data extracted from prior work done on the average VAS-Pain scores for TKA patients.

The statistical model for this investigation to be utilized in this investigation is a 2(Treatment) x 2(Time-point) mixed model analysis of covariance with repeated measures, co-varied on pre-operative VAS scores recorded on the day of surgery. Although there will be several days of VAS recorded out to 14-days post-surgery, the statistical question for pairwise comparisons will be to determine (1) how pain recorded on each subsequent day compares back to initial baseline (pre-operative) values within each group (treatment vs control) and (2) how each group compares to each other at the same measurement time-point. Therefore, each subsequent day will be modeled separately against the baseline value.

From the reference cited above, the 3-day average VAS score immediately following TKA was 3.2 cm (standard deviation, 2.0cm). The minimum detectable change (MDC) to detect will be set at 1.6cm as described in the literature.

The primary hypotheses of the study is that the treatment group will experience a reduction in post-operative pain compared to the control group. Based on the previous literature listed above, for a power analysis of 2 groups across 2 time-points, to detect a MDC of 1.6cm at a statistical

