power of 0.9 ( $\alpha=0.05$ ), we will require a total of 35 patients per group (total of 140 observations). To account for a potential patient dropout rate of ~20%, we will aim to recruit 42 patients per group for a total of 84 patients.

The aforementioned statistical analysis will be performed at the end of each year to evaluate the efficacy of the intervention and to identify potential outliers in the data or any possible errors in data entry. Yearly analysis using the same statistical modeling will also be performed for our secondary outcome measures (tissue biomarkers) in order to prevent potential tissue sample and biochemical reagent degradation over time and to confirm the accuracy of the tissue analysis procedure performed.

Additionally, the study will stop recruiting if adverse effects is significantly different between the two treatment groups, or greater than the previously specified risks listed within the informed consent and protocol or if a new unanticipated adverse effect is discovered. Recruitment will be suspended if there are 5 similar adverse events in a row. The most serious risks include respiratory depression, apnea, circulatory depression, respiratory arrest, shock, and cardiac arrest. These risks are <1% of the population. More frequent adverse effects include sedation, lightheadedness, dizziness, nausea, vomiting, and constipation. Patients will be monitored for these side effects in the immediate post-operative period.

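### The primary pain hypothesis has no named day, summary measure or success rule: the groups are compared in up to 14 separate daily models without multiplicity control, and the power statement covers one such comparison.

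*Combined protocol and SAP*

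**What the plan says.** Section 1 gives Aim 1 as "IO morphine will significantly reduce patient pain in the post-operative period after primary TKA". The statistical paragraphs of Section 3 (placed under the blood-sample heading) take VAS pain as the primary outcome and state the primary hypothesis as "the treatment group will experience a reduction in post-operative pain compared to the control group". Neither statement attaches a day, a window or a summary.

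The symptom journal in Section 3 asks patients to "Record daily pain levels using a validated pain scale for 14 days post op". The model is a 2 (treatment) by 2 (time-point) repeated-measures analysis of covariance, adjusted for pre-operative VAS. It is to answer two questions: how each day compares with baseline within each group, and "how each group compares to each other at the same measurement time-point". The paragraph concludes: "Therefore, each subsequent day will be modeled separately against the baseline value".

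The planning figures come from a cited source, where "the 3-day average VAS score immediately following TKA was 3.2 cm (standard deviation, 2.0cm". The power statement is "for a power analysis of 2 groups across 2 time-points, to detect a MDC of 1.6cm" with power 0.9 and alpha 0.05, and concludes that "we will require a total of 35 patients per group (total of 140 observations".

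No section names a primary day, an average or area under the curve, a testing order, a global test, a multiplicity adjustment or a rule for declaring success.

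**The concern.** The main confirmatory claim has no defined test. With a separate model for each day, the trial produces up to 14 between-group p-values for one hypothesis, and nothing says how they combine into a conclusion. The plan does not rule out claiming success from whichever day is significant. It also gives no basis for answering a critic who says that a genuine effect on one day should not count. Once unblinded results have been seen, a choice of day can no longer be credibly presented as prespecified.

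The power statement does not settle the matter, because it describes a single baseline-plus-one-day comparison. Its SD belongs to a 3-day average, which the plan does not adopt as an outcome.

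**Working it through.** **1. Reproduce the plan's sample size.** Inputs from Section 3: difference 1.6 cm, SD 2.0 cm, alpha 0.05, power 0.90. Sidedness is not stated.

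- n per group = 2 (z₀.₉₇₅ + z₀.₉₀)² SD² / δ² = 2 × (1.960 + 1.282)² × 2.0² / 1.6² = 32.8, so 33. The t-based figure is 34.
- Power at 35 per group is 91.7% (normal) or 91.0% (t).
- A one-sided test would need only 27, so the plan's figure is consistent with a two-sided test.
- 35 × 2 groups × 2 time-points = 140 observations, as stated.

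The planned size therefore matches one unadjusted two-group comparison.

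**2. Count the tests.** One between-group comparison per daily model over 14 days gives up to 14 tests. The within-group comparisons with baseline are additional.

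**3. Chance of a false claim in morphine's favour, if any significant day counts.** Each day is tested at two-sided 0.05 with no true effect, so one test gives 2.5%. For independent days, 1 − 0.975¹⁴ = 29.8%. Daily pain scores are correlated, but the documents give no value, so correlations are assumed. The first three columns simulate correlated normal test statistics (400,000 draws). The last simulates an analysis of covariance of each day on group and baseline, with 35 per group and an assumed baseline correlation of 0.3 (20,000 trials).

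| Between-day correlation | 3 days | 7 days | 14 days | 14 days, ANCOVA |
|---|---|---|---|---|
| Exchangeable 0.4 | 6.6% | 12.7% | 19.9% | 21.7% |
| Exchangeable 0.7 | 5.5% | 8.9% | 12.4% | 13.1% |
| AR(1) 0.7 | 5.7% | 11.3% | 20.2% | 21.5% |
| AR(1) 0.9 | 4.4% | 7.3% | 11.8% | 12.6% |

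At exchangeable 0.9 the 14-day rate is 7.0%. In the ANCOVA simulation, a single test on day 1 gives 2.5-2.6%, and a single test on the mean of days 1-3 gives 2.4-2.5%.

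**4. What adjustment over 14 days would cost.** Bonferroni alpha is 0.05 / 14 = 0.00357. Power per day at 35 per group falls to about 63% (t) or 67% (normal). Holding 90% would need about 58 (t) or 56 (normal) evaluable patients per group.

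**5. Does the planning SD fit a single day?** If 2.0 cm is the SD of each patient's 3-day mean, then single-day SD = 2.0 / √(mean of the 3 × 3 correlation matrix). For exchangeable 0.4, the mean is (3 + 6 × 0.4) / 9 = 0.60, giving 2.0 / √0.60 = 2.58 cm.

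| Correlation | Single-day SD | Power for 1.6 cm, 35 per group, no covariate gain |
|---|---|---|
| Exchangeable 0.4 | 2.58 cm | 72% |
| Exchangeable 0.7 | 2.24 cm | 84% |
| AR(1) 0.7 | 2.30 cm | 82% |
| AR(1) 0.9 | 2.09 cm | 88% |

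The planned baseline covariate recovers part of this loss. It multiplies the SD by √(1 − r²). With r = 0.3 the range becomes about 76-91%, and with r = 0.5 about 84-95%.

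**The case against.** The plan never says that one significant day confirms the hypothesis. It calls the daily contrasts pairwise comparisons, and the error rates above follow from an any-day rule, assumed correlations and an assumed number of tested days. That is correct, and the rates should be read as illustrations. The objection does not supply the missing rule, however: no other reading is stated either.

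The 3-day average could be taken as the implied endpoint. But it appears only as a figure from the cited source, and modelling each day separately contradicts it. If it is what the sponsor intends, one sentence would say so.

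The simulated analysis of covariance is simpler than the planned 2 by 2 mixed model, in which baseline is both a time-point and a covariate. The 13-22% is therefore an approximation to the plan as written. It agrees closely with the model-free figures for correlated test statistics.

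The power argument is the weakest part. Whether 2.0 cm is an SD of patient-level 3-day means or a daily SD cannot be determined from the protocol, and with the covariate the power range reaches or spans 90%. No shortfall is established, only a mismatch that the plan leaves open.

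Section 3 also repeats the efficacy analysis yearly, and Section 13 confirms a yearly interim analysis, with no adjustment stated. That is a separate source of error. Naming one primary test does not cure it, and the rates above do not include it.

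**Conclusion.** The concern holds. From the text alone, the primary test is undefined: one general pain hypothesis, up to 14 separate daily between-group comparisons, no multiplicity control, and a sample size for one comparison. This part needs no assumption.

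Its possible size depends on an any-day reading at two-sided 0.05 per day and on assumed correlations. Over 14 days the chance of a false claim in morphine's favour is then about 12-20%, with a wider range of 7% (exchangeable 0.9) to 30% (independence), against 2.5%. With three days tested it is about 4-7%, and with seven about 7-13%. Even the most favourable 14-day case shown nearly triples the single-test error. The stated 91% power applies to a single day only if an SD of 2.0 cm applies to that day.

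This should be corrected before any unblinded analysis, because it concerns the trial's main claim.

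**What to change.** Before any unblinded analysis, including the first yearly one, the sponsor should:

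- Name one primary between-group test at two-sided 0.05, adjusted for pre-operative VAS, on a single prespecified day or summary, and state that this test alone decides the primary hypothesis. Mean VAS over the first three post-operative days is one example. It corresponds to the measure from which the planning SD was taken. The text should say exactly which days count.
- Report the daily differences to day 14 as secondary estimates with confidence intervals from one repeated-measures model.
- Treat within-group changes from baseline as descriptive, since they do not compare the treatments.
- Restate the power for the chosen measure and say what the 2.0 cm SD describes. The planned 35 evaluable per group suffices if that SD applies. If a single day is chosen, recheck the power.

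The cost is analysis-plan wording, with no new data and, on the 3-day mean with SD 2.0 cm, no new patients. The downside is that single-day results lose confirmatory status, and an effect confined to days outside the chosen window could not be claimed as the primary result. Error control across the yearly analyses needs its own provision.

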## 3. Study Design

This study is a double-blind randomized controlled trial with two arms. The control group will receive an intraosseous (IO) injection of antibiotics as per [name], [name], and [name] standard of care for primary TKA patients. The experimental group will receive an IO injection of antibiotics mixed with 10 mg of morphine. A research coordinator on the study team will inform the circulator nurse present in the OR during the study patient's case about which group (morphine or no morphine) the patient is in. The circulator nurse will then be instructed to place morphine into the surgical field during the mixing process of the intraosseous solution without notifying the surgeon to ensure the double blind. Patient's post-operative pain levels, pain medication consumption, side effects to pain medications, and range of motion will be recorded for 14 days following surgery.

Patient outcomes will also include pain levels, post-operative pain medication use, and post-operative ROM.

The anticipated total number of participants is 84 with 42 patients being in each group. The maximum number of subjects who will be enrolled is 84 patients (i.e. give consent to participate) at this site.

Participants will be randomized into either the control group or the experimental group by an excel-based software program.

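### Recruiting 42 per group keeps the required 35 only up to about 17% dropout, not the stated figure of about 20%; the effect on power is small

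*Combined protocol and SAP*

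**What the plan says.** The power calculation is in Section 3 of the combined protocol and SAP, in the text that follows the subheading on baseline and post-operative blood samples. It takes its spread from earlier work, in which "the 3-day average VAS score immediately following TKA was 3.2 cm (standard deviation, 2.0cm"), and sets the effect size thus: "The minimum detectable change (MDC) to detect will be set at 1.6cm". At power 0.9 and alpha 0.05 it concludes that "we will require a total of 35 patients per group".

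The next sentence makes the step to recruitment: "To account for a potential patient dropout rate of ~20%, we will aim to recruit 42 patients per group", which gives 84 in total. The study design text at the start of Section 3 repeats the target ("The anticipated total number of participants is 84 with 42 patients being in each group") and makes 84 the maximum enrolment. No inflation formula is given, and nothing else in the document explains how 35 became 42.

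**The concern.** Dropout happens among the patients who are recruited. A target that allows for a 20% loss must therefore still leave 35 after 20% of the recruited patients are gone. The figure of 42 looks instead like 35 with 20% added on top, which is a smaller allowance.

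What is at stake is the accuracy of the only sentence that justifies the recruitment target. A team relying on it would believe that 8 losses in a group (19%) still leave 35, when they leave 34. Because 84 is also the enrolment maximum, losses beyond 7 per group could not be replaced under the current text. If the true allowance were far below the stated one, the planned power would also be in doubt, so the size of the gap has to be checked.

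**Working it through.** **Inputs (all from Section 3)**
- Evaluable patients required: 35 per group
- Stated dropout: about 20%
- Recruitment target: 42 per group, 84 in total (also the maximum)
- Effect size 1.6 cm, SD 2.0 cm, alpha 0.05, power 0.9
- Sidedness is not stated. A two-sided test is assumed.

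**Step 1: the plan's 35.** The unadjusted two-sample normal formula is n = 2 × (z₀.₉₇₅ + z₀.₉₀)² × (SD / difference)². With the plan's inputs this is 2 × (1.960 + 1.282)² × (2.0 / 1.6)² ≈ 32.8, so 33 per group. The noncentral t calculation gives 34. The stated 35 is within 2 patients of both. A one-sided test gives 27, which does not match, so the two-sided assumption fits the plan better.

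**Step 2: the plan's 42.**
- Adding 20% to the evaluable number: 35 × 1.20 = 42, exactly the stated figure.
- Allowing for a 20% loss from those recruited: 35 / (1 − 0.20) = 43.75, so 44 per group (88 in total).

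**Step 3: what 42 delivers.**
- Remaining at 20% loss: 42 × 0.80 = 33.6, a shortfall of 35 − 33.6 = 1.4 per group.
- Largest loss that leaves 35: 1 − 35/42 = 16.7%.

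| Losses per group | Share of 42 | Remaining |
|---|---|---|
| 7 | 16.7% | 35 |
| 8 | 19.0% | 34 |
| 9 | 21.4% | 33 |

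**Step 4: effect on power.** This is a rough check for an unadjusted, two-sided comparison of two groups at one time-point, with a difference of 1.6 cm and SD 2.0 cm. In the normal approximation, power = Φ(1.6 / (2.0 × √(2/n)) − 1.96).

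| n per group | Normal approximation | Noncentral t |
|---|---|---|
| 35 | 0.917 | 0.910 |
| 34 | 0.910 | 0.902 |
| 33.6 | 0.906 | 0.898 |
| 33 | 0.901 | 0.893 |

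Going from 35 to 33.6 costs 1.1 to 1.2 percentage points.

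**Step 5: sensitivity.** The planned model is a baseline-adjusted repeated-measures analysis whose software settings are not given, so two variations were tried.
- If 35 per group gave exactly 0.90, power at 33.6 would be about 0.888 (0.882 at 33, 0.891 at 34).
- If adjustment for baseline is credited with an assumed correlation of 0.3 to 0.5 between baseline and outcome, power at 33 to 34 per group is about 0.92 to 0.96.

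**The case against.** The strongest reply is that the rate is given only as approximate and as a potential rate. Seven losses, 16.7%, leave exactly 35, and 16.7% does become 20% when rounded to the nearest ten. That reading is possible but generous. Both whole-patient losses nearest 20% fall below 35, and the exact match of 42 with 35 × 1.2 makes a multiplication in place of a division the likelier origin, although the document does not confirm it.

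A second reply is that nothing of substance follows. This largely stands: 35 already sits 1 to 2 patients above what the inputs need in the unadjusted calculation, so 33 or 34 retained patients still give close to 90% power. It limits the weight of the point without making the sentence correct.

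Third, the power check is not the sponsor's model. That also stands. If the sponsor's model gives exactly 0.90 at 35, a 20% loss takes it slightly below, to about 0.89. The statement that power is little affected therefore rests on a rough check.

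Fourth, dropout is not defined. Pain is recorded daily for 14 days and each day is modelled separately against baseline, so a patient who stops early may still contribute the early days. The figure of 33.6 is then a worst case for those days, and it also assumes equal loss in both groups. Neither point reconciles 42, 35 and 20%.

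**Conclusion.** The concern holds and is minor. By the plan's own figures, 42 per group covers 16.7% dropout rather than about 20%. At 20% the shortfall is 1.4 patients per group (1 at 8 losses, 2 at 9). This part is arithmetic on stated numbers and needs no assumption beyond counting a dropout as a patient lost to the analysis, with equal loss in the two groups.

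The planned power is not materially affected: about 0.89 to 0.91 at 33 or 34 per group in the unadjusted check. If 35 gives exactly 0.90, power is about 0.88 to 0.89 at those numbers. That part assumes a two-sided test and does not reproduce the planned repeated-measures model.

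**What to change.** Keep 84 patients and replace the sentence on dropout with wording such as: *42 per group allows for about 17% dropout while retaining 35 per group; at 20% dropout about 33 to 34 per group would remain.* Add a power figure for the 20% case only if the sponsor recomputes it under its own planned model.

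The cost is one restated sentence. Recruitment, the maximum of 84, the design and the analysis stay as they are. Raising the target to 44 per group (88 in total) would also make the sentence true, but it would mean lifting the enrolment maximum, which is out of proportion to a power difference of about one percentage point.

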This study will not require the patient to attend any additional study visits. The expected amount of time the patient for the patient to complete all study related items including filling out the symptom journal and answered pre/post-op surveys is approximately 90 minutes. The patient will participate in the study for a total of 52 weeks. The anticipated duration to enroll all study subjects is 18 months. The estimated date for the investigators to complete primary analyses is 2.5 years following the initiation of the study.

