### 13. Data Safety Plan

The study will be monitored by clinicians involved in the study. Interim analysis will be performed yearly.

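### The yearly efficacy run gives one by-arm look at pain data about month 12, and the plan neither calls it non-confirmatory nor keeps it from the blinded surgeons

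*Combined protocol and SAP*

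**What the plan says.** All references are to the combined protocol and SAP.

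- **The yearly run.** The statistical text of Section 3 (under the blood-sample subheading) says "The aforementioned statistical analysis will be performed at the end of each year to evaluate the efficacy of the intervention". The same sentence adds a search for outliers and data-entry errors.
- **What is run.** The model is the one set out just before it. One of its two stated questions is "how each group compares to each other at the same measurement time-point", and "each subsequent day will be modeled separately against the baseline value". It is therefore a between-arm efficacy comparison.
- **Biomarkers.** "Yearly analysis using the same statistical modeling will also be performed for our secondary outcome measures". The reasons given are degradation of samples and reagents, and accuracy of the assay procedure.
- **Monitoring.** Section 13 reads in full: "The study will be monitored by clinicians involved in the study. Interim analysis will be performed yearly".
- **Stopping.** The only stopping or suspension rules in Section 3 are for adverse effects, for example "the study will stop recruiting if adverse effects is significantly different between the two treatment groups".
- **Timeline (Section 3, Study Intervention).** "The anticipated duration to enroll all study subjects is 18 months"; each patient takes part for 52 weeks; "The estimated date for the investigators to complete primary analyses is 2.5 years following the initiation of the study".
- **Blinding and access.** Section 3 calls the trial double-blind and has the morphine added without the surgeon being told. Section 5 restricts study data to the research team. Section 3, in the tourniquet paragraph, counts the three surgeons as members of that team.

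Alpha of 0.05 appears once, in the fixed-sample calculation that gives 35 per group. No section says whether a yearly efficacy result may be claimed or acted on, gives an efficacy boundary, or restricts access to results by arm.

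**The concern.** Two separate things are left open.

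1. **Status of the result.** A reader shown a month-12 difference with p<0.05 could not tell from the protocol whether it was a confirmatory finding or a by-product of data checking. If it could be claimed, there are two chances of a false positive, and the 0.05 behind the sample size no longer describes the trial.
2. **Who sees it.** Followed as written, the plan produces efficacy results by arm while patients are still being enrolled. It gives monitoring to the study's own clinicians without saying whether these include the surgeons who are kept blind in theatre. This gap remains even if nobody would ever claim the month-12 result.

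The other purposes of the yearly run (outliers, entry errors, sample and reagent degradation, assay accuracy) need no comparison between arms. The by-arm run therefore carries a risk without serving any decision that the plan names.

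**Working it through.** **Inputs from the documents:** alpha 0.05, power 0.9, difference 1.6 cm, SD 2.0 cm, 35 evaluable and 42 recruited per group, 84 in total, 18 months of enrolment, 14 days of pain scores, 52 weeks of participation.

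**Assumptions:** two-sided testing (the plan does not state sidedness), uniform accrual, and one pain comparison taken alone.

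**1. The plan's own figure.** n per group = 2 × (1.960 + 1.282)² × 2.0² / 1.6² = 32.8, so 33; the t-based calculation gives 34. The stated 35 is consistent with this. Power at 35 per group is 0.917 (normal) or 0.910 (t). This is a single-analysis calculation with no allowance for an interim look.

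**2. How many interim looks.** Enrolment ends at month 18, and the last 14-day journal about half a month later. Only the month-12 run falls before the pain data are complete. A month-24 run would use the full pain data.

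- Recruited by month 12: 84 × 12/18 = 56, leaving 84 − 56 = 28 to enrol.
- With complete 14-day data at month 12: 84 × 11.5/18 ≈ 54.
- Information fraction t: 12/18 = 0.667, or 11.5/18 = 0.639 allowing for the 14-day lag.

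**3. Type I error.** Under the null, the interim and final statistics are bivariate normal with correlation √t. The probability of p<0.05 at either look is 1 − P(|Z₁| ≤ 1.96 and |Z₂| ≤ 1.96).

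| What counts | t = 0.667 (√t = 0.816) | t = 0.639 (√t = 0.799) |
|---|---|---|
| Final analysis only | 0.050 | 0.050 |
| Either look | 0.0770 | 0.0781 |
| Either look, benefit direction only (0.025 for one analysis) | 0.0385 | 0.0391 |

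Cross-check at t = 0.667: the chance that the interim is significant and the final is not is 0.0270, and 0.0500 + 0.0270 = 0.0770. A simulation of t-tests on accumulating data (23 then 35 per arm, 400,000 trials) gave 0.0777 for either look and 0.0500 for the final alone.

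Sensitivity: 0.083 at t = 0.50 and 0.073 at t = 0.75. If accrual slipped so that two interim runs came before the full data, the figure would be about 0.097 to 0.107.

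**4. Chance of a visible positive result at month 12 if the planned effect is real.** Evaluable per arm: 35 × 12/18 = 23.3, so 23; or 35 × 11.5/18 = 22.4, so 22 with the lag. Non-centrality = 1.6 / (2.0 × √(2/n)).

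- n = 23: non-centrality 2.71, 44 df, power 0.756.
- n = 22: non-centrality 2.65, 42 df, power 0.736.

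This is an unadjusted t-test using an SD that the plan takes from a 3-day average score. The plan's daily models adjust for pre-operative pain, so actual power could differ.

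**5. Where knowledge of the result could act.** Pain is recorded by patients in a journal (Section 3), and a group-level result does not reveal any one patient's allocation. Range of motion comes from therapist notes and the 2-week visit (Section 3, Study Intervention), and post-operative management is in clinicians' hands. Those two are exposed. The documents give nothing from which to size the effect.

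**The case against.** The strongest reply is that a look with no efficacy action attached spends no alpha. The only stopping rules concern adverse effects and the primary analyses are placed at 2.5 years, so the natural reading is that only the final result counts. This largely stands: it makes the inflation conditional. But it is an inference. No section says it, and the stated purpose of the yearly run is to judge efficacy.

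Four stronger readings are tempting, and the documents do not support them.

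- **Repeated looks during enrolment.** The word yearly suggests several. On the stated 18 months there is one; more arise only if accrual slips.
- **A conflict between yearly analysis and the 2.5-year date.** There is none: 18 months plus 52 weeks is 2.5 years.
- **Biased primary pain scores.** Patients score their own pain and group results do not unblind individuals, so direct bias there is unlikely.
- **A need for a group-sequential boundary.** The plan models each post-operative day separately and names no single primary comparison, so a nominal level such as an O'Brien-Fleming value would have nothing definite to apply to.

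It can also be said that Section 5 already limits access. It does, but only to the research team. That team includes the surgeons, and Section 5 says nothing about results by arm.

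**Conclusion.** The point holds as a cheap improvement, not as a flaw that undermines the trial. The plan schedules one by-arm efficacy analysis about month 12 of an 18-month double-blind enrolment, without giving the result's status and without withholding it from the blinded surgeons.

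A reader might infer that the trial's error rate is 7.7 to 7.8%. That is so only if a month-12 p<0.05 could be claimed alongside the final one; otherwise it is 5%. Both figures are for one comparison, two-sided, with uniform accrual. They exclude the multiplicity from modelling each post-operative day separately, which is a different issue that this change does not address.

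The access gap does not depend on that condition. If the planned effect is real, a significant month-12 comparison is likely (power about 0.74 to 0.76) with 28 of 84 patients still to enrol. The possible consequence is limited to clinician management and range of motion, and its size cannot be estimated from the documents.

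**What to change.** **Section 3.** Replace the yearly efficacy run and the yearly biomarker comparison with wording such as: *Yearly review is limited to pooled data without treatment labels: outliers, entry errors, missingness and assay quality control. Between-arm efficacy and biomarker comparisons are made once, at the final analysis.* The assays themselves may still be run yearly, so the concern about sample and reagent degradation is met.

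**If a yearly by-arm look is kept,** add: *Yearly results are non-confirmatory; they cannot be claimed and cannot stop or change the trial for efficacy.*

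**Section 13.** State that results by arm, including any adverse-effect comparison that the existing stopping rule needs, are not shown to the blinded surgeons or to staff who enrol patients. Clinical judgement on adverse events stays with the clinicians, as that section assigns it.

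**Cost.** A few sentences in two sections, with no change to sample size or to the final test level. The sponsor gives up an early efficacy read-out to which the plan attaches no decision. Someone outside the blinded and enrolling staff must handle any by-arm comparison. The documents do not show who that would be, so the sponsor should confirm that such a person is available.
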